7.6.2 Consent Form

The informed consent document for this study is maintained as a separate document.

7.6.3 HIPAA

Information about study subjects will be kept confidential and managed according to the requirements of the Health Insurance Portability and Accountability Act of 1996 ([HIPAA](#)). Attached/submitted as part of our application is a signed subject authorization form that includes information collected during this study as well as from medical record data will be used by the researchers and research staff as a part of this investigation. A HIPPA authorization form is attached to this protocol as an Appendix.

7.6.4 Revoking Consent

In the event that a subject revokes authorization to collect or use PHI, the investigator, by regulation, retains the ability to use all information collected prior to the revocation of subject authorization. For subjects that have revoked authorization to collect or use PHI, attempts should be made to obtain permission to collect at least vital status (i.e. that the subject is alive) at the end of their scheduled study period.

7.6.5 Costs to the Subject

There will be no costs to the participants for this study, any costs occurred during this research study will be covered by the grant funding mechanism.

7.6.6 Payment for Participation

Participants will be paid \$50 in cash at the baseline visit as well as another \$50 cash at the final (post-intervention) visit. Those who complete the intervention will receive a total of \$100 cash. At the instructional visit, participants will be provided with exercise equipment (towel, band, duffle bag, resistance bands, and dumbbells) that they will use for the intervention and will be allowed to keep after the intervention has completed. Any parking costs required for the in-person visits will be covered as a part of the study.

7.7 Early Withdrawal of Subjects

7.7.1 When and How to Withdraw Subjects

Participants may withdraw from the study prior to expected completion due to safety reason, losses to follow up, failure of subject to adhere to protocol requirements, subject consent withdrawal, etc.

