4.1.1 Primary Study Endpoints

The primary endpoint is adherence to prescribed exercise sessions as measured using exercise logging and video sessions of exercises.

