7.7.2 Data Collection and Follow-up for Withdrawn Subjects

Data will be attempted to be gathered from participants who have withdrawn from the study to collect their data prior to their withdrawal, including emails from the research staff and telephone calls.

Withdrawn subjects will be analyzed using an intent to treat analysis, therefore maximizing the amount of data is paramount to success. However, if participants cannot be contacted after 3 attempts from the study team (both telephone calls and emails) then the participants will be considered lost to follow-up.

8 Study Procedures

Wait list interventions

After being randomized to the wait-list group, participants will be scheduled for their 10 week follow up visit. The wait list arm will not have the additional five week follow up that the exercise arm receives. Participants will be reminded that at that final visit, participants will complete the same study measures (body composition, functional fitness testing, blood sample collection, and anthropometrics) and will also receive study materials at the end of their wait list period. Participants in the wait list group will also complete accelerometer (Actigraph) assessments at three study points: Early in the intervention near the instructional visit, at the mid-way (5-week) mark, and before the final visit. These accelerometers will be sent and received via mail and participants will receive instructions on how to wear, use and send to us during the instructional visit.

Exercise interventions

After being randomized to the exercise (intervention) arm, participants will be scheduled for an instructional visit with the study coordinator within a week of randomization. At that visit, participants will be instructed to wear comfortable clothes and shoes for learning the exercises. The instructional visit includes going through each exercise of the intervention (see Table below) to learn the movement, learn the muscle groups involved, and to learn how to monitor themselves by tracking their progress via logs. This instructional visit should take 60-90 minutes, and each participant will receive a summary sheet of her starting point at each exercise with respect to intensity and progressions/regressions. For example, a participant may be starting on a blue resistance band for biceps curls, but the squats may simply be body weight at this time. Table below outlines the exercises for the intervention.

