 - **When collected:** Baseline, mid-point (~5 weeks), final visit (~10 weeks)
- **Self-efficacy.** This will be assessed using the validated self-efficacy for exercise scale, modified for specificity to strength training.³⁴ These measures will be repeated at the study mid-point (5 weeks) to assess changes over time.
 - **When collected:** Baseline, mid-point (~5 weeks), final visit (~10 weeks)
- **Adherence.** Compliance and adherence will be measured via detailed exercise logs. A participant needs to complete at least 50% of the prescribed exercises in a session to be considered adherent to the session.
 - **When collected:** ongoing, logs will be completed throughout the intervention and submitted at the final visit
 - Additionally, for those in the intervention arm, we will ask that they continue to conduct the prescribed exercises for an additional five weeks after study completion. Participants will still submit paper logs, and this adherence measure will allow for study of adherence without prescribed check-ins from the study coordinator over the five week period.
- **Acceptability.** Participants will participate in a semi-structured qualitative interviews with the study coordinator. Interviews will be recorded, transcribed and coded to identify content themes. These interviews will be used to collect qualitative information and overall satisfaction with the intervention, as well as areas to improve with future interventions and barriers to participation.
 - **When collected:** Final visit (~10 weeks)

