12.32 Subject Stipends or Payments

Participants will be paid \$50 in cash at the baseline visit as well as another \$50 cash at the final (post-intervention) visit. Those who complete the intervention will receive a total of \$100 cash.

13 Publication Plan

The primary responsibility for publication of the results of this study are the investigators at UW Madison ([name]). Neither the complete nor any part of the results of the study carried out under this protocol, nor any of the information provided by the sponsor for the purposes of performing the study, will be published or passed on to any third party without the consent of the study sponsor. Any investigator involved with this study is obligated to provide the sponsor with complete test results and all data derived from the study.

14 Protocol implementation timeline and contingency plans

There are three primary concerns for this research design and there are listed preliminary contingency plans if these concerns come to fruition:

- The primary concern is a lack of subjects or low accrual to study participant goals for site numbers.
 - If there is insufficient or slow recruitment through a clinical route, we plan to reach out to community support groups such as Gilda's Club to bolster recruitment numbers. This strategy will not replace the clinical route, but may increase participant enrollment.
- The secondary concern is high attrition in the treatment group and potential losses to follow up over the course of the 10-week intervention. Although this is a lower probability event, we will utilize the following contingency plans:
 - Deploy follow ups using a support person for the participant that we can contact if the participant is not contacting study staff or seems to be lost to follow up
 - At the start of the study, we will collect multiple email addresses and phone numbers from

each participant to avoid this problem *a priori*.

- Finally, we may have poor adherence and compliance to the protocol.
 - We have pre-scheduled check-ins during the course of the intervention to avoid this issue
 - However, we will deploy additional health coaching if necessary where participants are really struggling with adherence
 - Participant satisfaction surveys will be used at the end of the intervention to evaluate the quality of the study to learn and improve for the future if adherence is very high

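### Section 7.7.1 makes non-adherence a ground for leaving a study whose primary endpoint is adherence, and the intent-to-treat statement in 7.7.2 is not carried into the primary analysis in 9.3.1

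*Combined protocol and SAP*

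**What the plan says.** Section 4.1.1 is explicit: "The primary endpoint is adherence to prescribed exercise sessions", measured by exercise logs and video sessions. Section 9.3.1 tests the percentage of prescribed sessions completed against 90% with a one-sample t-test, and tests retention against 90% in the same way.

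Section 7.7.1 lists as reasons for leaving early "safety reason, losses to follow up, failure of subject to adhere to protocol requirements, subject consent withdrawal, etc". It gives no threshold and names no one who decides.

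Section 7.7.2 follows directly: "Withdrawn subjects will be analyzed using an intent to treat analysis, therefore maximizing the amount of data is paramount to success". The data to be sought, by email and telephone, are those of "participants who have withdrawn from the study to collect their data prior to their withdrawal". No assessment after withdrawal is planned.

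Section 8.1 says of the adherence logs that "logs will be completed throughout the intervention and submitted at the final visit". Table 3 also lists weekly adherence logs and coaching-call completion as data collected during the intervention.

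Section 9.3 defines three populations (all-randomized, all-treated, protocol-compliant), but 9.3.1 assigns none of them to the primary analysis. Section 10.2.1 leaves missing-data handling to be chosen later.

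Section 14 has a different response to poor adherence: "we will deploy additional health coaching if necessary where participants are really struggling with adherence".

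**The concern.** In most trials, withdrawing a participant for non-compliance affects how much is known about some other outcome. Here non-compliance with the sessions is the outcome. A ground for leaving that depends on it takes participants from the low end of the distribution being estimated. Without a threshold, the same behaviour can be recorded either as low adherence in a retained woman or as a loss to retention.

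Two results are at stake. The first is the adherence percentage, which is meant to show whether the programme is feasible enough to take into a larger study. The second is the set of week-10 body composition, fitness and biomarker measures. If the women who trained least leave before week 10, the exercise arm's values describe those who trained more. Wait-list women are not prescribed sessions before their final visit, so they cannot be lost through missed exercise.

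**Working it through.** The plan has no power or precision calculation to reproduce; section 9.1 says the sample of 40 was chosen for feasibility. The check therefore compares the relevant sections and then shows how sensitive the result is.

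**Inputs from the documents**
- Total sample 40 (section 9.1), randomized 1:1 (section 8.5): 40/2 = 20 exercise women.
- Two sessions a week for 10 weeks (section 8): 2 × 10 = 20 prescribed sessions each.
- Target for both adherence and retention: above 90% (section 9.3.1). Alpha and sidedness are not stated.

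**Does 7.7.2 together with 9.3.1 settle how a withdrawn low adherer counts?**
- Population: not settled. All-randomized would include her. Protocol-compliant, the only population defined by allocation to exercise, has no minimum adherence but needs at least one set of data elements, so a woman whose data are not recovered could drop out of it.
- Denominator: not settled. Nothing says whether sessions after withdrawal are missed or missing.
- Logs: other sources exist, but no rule says how an unreturned log is scored.
- Week-10 measures: not secured. An intent-to-treat label cannot supply values that were never collected.

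**Assumed adherence values** (the documents give no distribution)

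Let k of 20 women be low adherers completing a fraction L of sessions, with the others averaging 95%.

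Mean with all kept = [(20 − k) × 95% + k × L] / 20. Mean with the k women lost = 95.0%.

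| k | All kept, L = 25% | All kept, L = 50% | The k lost | Retention overall | Retention in exercise arm |
|---|---|---|---|---|---|
| 1 | 91.5% | 92.8% | 95.0% | 39/40 = 97.5% | 19/20 = 95% |
| 2 | 88.0% | 90.5% | 95.0% | 38/40 = 95% | 18/20 = 90% |
| 3 | 84.5% | 88.3% | 95.0% | 37/40 = 92.5% | 17/20 = 85% |

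For k = 2 and L = 40%: (18 × 95 + 2 × 40)/20 = 1,790/20 = 89.5% with all kept, against 95.0% with the two lost. If the other 18 women lie between 90% and 100%, a one-sided t-test against 90% (one-sided is an assumption) gives p = 0.55 with all kept and p < 0.001 with the two lost.

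**The denominator alone.** Suppose each of the two women completed 8 sessions and left after week 5, when 10 had been prescribed. Over 20 sessions she scores 8/20 = 40%; over the 10 before withdrawal, 8/10 = 80%. With both women still in the analysis, the mean is 89.5% on the first count and (18 × 95 + 2 × 80)/20 = 1,870/20 = 93.5% on the second. Including withdrawn women is therefore not enough without a counting rule.

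**The case against.** The strongest answer is section 7.7.2. It comes directly after the withdrawal grounds, commits to intent to treat, and has staff chase data from before withdrawal. A reader might infer from 7.7.1 that low adherers are to be taken out of the adherence result. The documents do not say that, and their stated intent is the opposite. This objection stands against that reading. It does not close the gap, because the commitment is not turned into a population, a denominator or a rule for missing logs.

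Other stronger readings are also not supported:
- **Staff may expel low adherers.** The sentence reads "Participants may withdraw from the study prior to expected completion due to safety reason". The section heading speaks of withdrawing subjects, and consent withdrawal is listed separately, so withdrawal by staff is a fair inference. It is not stated, and no decision-maker is named.
- **The ground applies to one arm only.** Protocol requirements also include accelerometer wear and the 10-week visit, which bind wait-list women. Only the part concerning exercise sessions is one-sided.
- **Logs are lost on withdrawal.** They may be, but coaching calls, video sessions and the retrieval effort in 7.7.2 offer other sources. Loss requires those to fail as well.
- **Section 14 contradicts 7.7.1.** Extra coaching followed by a possible withdrawal can be successive steps. The documents simply do not say how they relate.
- **A few withdrawals would leave both 90% targets met.** With three, overall retention is 92.5%, but the planned test gives t of about 0.59 (one-sided p about 0.28), and the exercise arm alone shows 85%. Retention would reveal part of the loss, though 9.3.1 does not say whether it is tested overall or by arm.

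It is also fair to say that this is a 40-woman pilot with a descriptive aim. That lowers the severity. It does not remove the point, since adherence against 90% is the planned primary result.

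**Conclusion.** The concern holds in limited form. The plan allows women to leave the study for the behaviour it sets out to measure. Its intent-to-treat statement is not specific enough to ensure that they count fully in the adherence result or are seen at week 10.

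With about 20 exercise women, two such losses are enough to matter: 89.5% becomes 95.0% if they drop out of the analysis, or 93.5% if they stay in but are scored only on sessions before withdrawal. These sizes rest on assumed adherence of 40% in two women and an average of 95% in the rest, and the 93.5% also assumes withdrawal after week 5. With a single low adherer in the range examined, the mean is above 90% either way. No figure stated in the plan is shown to be wrong, and nothing shows that such withdrawals will happen. This should be fixed, but it does not undermine the design.

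**What to change.** **Section 7.7.1.** Remove non-adherence to exercise sessions as a ground for withdrawal from the study. State that a woman who misses or stops sessions stays enrolled and keeps her scheduled assessments. The other listed grounds need not change. Clarify how this section and the extra coaching in section 14 fit together.

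**Section 9.3.1.** Carry over the intent-to-treat statement in operational terms:
- analyse adherence in all women randomized to exercise;
- fix the denominator at the 20 prescribed sessions;
- count sessions after withdrawal, for any reason, as not completed;
- add a sensitivity analysis for unreturned logs, for example scoring undocumented sessions as not completed and then from coaching-call records;
- report retention by arm as well as overall.

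The counting rule is needed even if 7.7.1 is changed, because women who withdraw consent or are lost to follow-up raise the same question.

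**Optional.** A row in the Appendix 1 tracking form for unscheduled coaching contacts would allow adherence to be shown separately for women who had only the planned calls.

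**Cost.** Protocol wording only. The adherence figure may come out lower, and a few non-adherent women stay on a visit schedule already planned for 40.

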7.7.2 Data Collection and Follow-up for Withdrawn Subjects

Data will be attempted to be gathered from participants who have withdrawn from the study to collect their data prior to their withdrawal, including emails from the research staff and telephone calls.

Withdrawn subjects will be analyzed using an intent to treat analysis, therefore maximizing the amount of data is paramount to success. However, if participants cannot be contacted after 3 attempts from the study team (both telephone calls and emails) then the participants will be considered lost to follow-up.

8 Study Procedures

Wait list interventions

After being randomized to the wait-list group, participants will be scheduled for their 10 week follow up visit. The wait list arm will not have the additional five week follow up that the exercise arm receives. Participants will be reminded that at that final visit, participants will complete the same study measures (body composition, functional fitness testing, blood sample collection, and anthropometrics) and will also receive study materials at the end of their wait list period. Participants in the wait list group will also complete accelerometer (Actigraph) assessments at three study points: Early in the intervention near the instructional visit, at the mid-way (5-week) mark, and before the final visit. These accelerometers will be sent and received via mail and participants will receive instructions on how to wear, use and send to us during the instructional visit.

Exercise interventions

After being randomized to the exercise (intervention) arm, participants will be scheduled for an instructional visit with the study coordinator within a week of randomization. At that visit, participants will be instructed to wear comfortable clothes and shoes for learning the exercises. The instructional visit includes going through each exercise of the intervention (see Table below) to learn the movement, learn the muscle groups involved, and to learn how to monitor themselves by tracking their progress via logs. This instructional visit should take 60-90 minutes, and each participant will receive a summary sheet of her starting point at each exercise with respect to intensity and progressions/regressions. For example, a participant may be starting on a blue resistance band for biceps curls, but the squats may simply be body weight at this time. Table below outlines the exercises for the intervention.

Table 2. Series of exercises, with progressions and regressions to increase/decrease difficulty.

Primary muscle group	Exercise	Progressions	Regressions
Thighs (quadriceps, hamstrings)	Body weight squats	
• Add resistance band• Holding dumbbells	
• Chair squats• Shortened range of motion
Calves (gastrocnemius, soleus)	Standing heel raises	
• Holding dumbbells• Elevate ball of foot	
• Shortened range of motion
Chest (pectoralis major & minor)	Standing chest press	
• Increase band tension	
• Reduce band tension
Back (trapezius, latissimus dorsi)	Seated banded row	
• Standing row• Increase band tension	
• Reduce band tension• Shorten range of motion
Abdominals (rectus & transversus abdominus)	Static v-sit hold with feet on floor	
• Elevate feet• Add rotation• Add dumbbell	
• Support with hands• Add lumbar support w/ towel
Shoulders (deltoids)	Seated banded press	
• Standing• Use dumbbells	
• Reduce band tension• Shorten range of motion
Biceps brachii	Seated banded curl	
• Standing• Add tension to band• Use dumbbells	
• Reduce band tension• Shorten range of motion
Triceps brachii	Seated arm extension	
• Increase band tension	
• Reduce band tension

During the study period, participants in the intervention arm will be instructed to complete the exercise routine twice a week for 10 weeks during the intervention, and also continued throughout the five week follow up period. There are eight video calls with the study coordinator to check in, to identify any issues or concerns with the exercises, and to finally monitor progress in the form of assessing volume/intensity/difficulty of each of the exercises. These calls are done over video so that the coordinator can build rapport with participants, and that participants can show

or demonstrate issues with exercises or their form. At the mid-point of the study, participants will receive an email with the questionnaires, so that the questionnaires will be done at baseline, at the study mid-point, and at the final visit.

Participants in the intervention group will also complete accelerometer (Actigraph) assessments at three study points: Early in the intervention near the instructional visit, at the mid-way (5-week) mark, and before the final visit. These accelerometers will be sent and received via mail and participants will receive instructions on how to wear, use and send to us during the instructional visit.

At the end of the 10 week period, participants will return to the UW campus for a final visit to repeat baseline study measures. At this time, intervention arm participants will also complete an exit-style interview with the study coordinator to help improve the intervention for future participants. This will be recorded, but anonymized upon transcription.

While the formal intervention period will be 10 weeks in duration, we will continue to follow those in the exercise arm for five weeks post-final assessment. This follow up period will consist of surveys to the participants assessing the frequency of the home-based resistance exercise, to determine if the behavior of exercise persists in the short-term following intervention conclusion.

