8.1 Measures

Below are the study measures that will be collected over the course of the intervention:

- Demographics and other participant characteristics: Participants will self-report age, race/ethnicity, marital status, education, and cancer characteristics (tumor type and stage, dates of diagnosis and treatment completion, treatment received). Clinical information will be confirmed with the medical record.
 - **When collected:** Baseline
- Accelerometer. Although aerobic and lifestyle PA (e.g., MVPA, steps) are not a focus of the intervention, they will be assessed to determine baseline PA level and identify whether uptake of resistance training is associated with changes in other PA types. Participants will wear the ActiGraph wGT3X-BT accelerometer (ActiGraph, Pensacola, FL) for 7 days during all waking hours. The ActiGraph is a gold standard method of objective activity assessment.^{26,27}
 - **When collected:** Baseline, mid-point (~5 weeks), final visit (~10 weeks)
- Biomarkers. Using a standardized protocol, participants will undergo a fingerstick to collect a peripheral blood sample to assess glycosylated hemoglobin (A1c) and c-Reactive Protein²⁸ via dried blood spots. The values for both A1c and CRP are highly correlated between dried blood spots and venipuncture.²⁹
 - **When collected:** Baseline, final visit (~10 weeks)
- Anthropometrics. Height, weight, waist and hip circumferences will be measured according to standard protocols.
 - **When collected:** Baseline, final visit (~10 weeks)
- Body composition. Resistance training can improve body composition even without weight loss. Body composition will therefore be assessed using dual-energy absorptiometry (DXA) using the enCORE Lunar iDXA software suite (GE Healthcare, Little Chalfont, UK). DXA provides a precise measure of fat mass, lean mass, total % body fat, and visceral fat and is sensitive to small changes from pre- to post-intervention.³⁰
 - **When collected:** Baseline, final visit (~10 weeks)

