8.4.4 Final Study Visit

Final Visit. All participants will return for follow-up assessments at 10 weeks. In advance, the participant will be mailed an accelerometer and 7-day PA log and will receive a link to complete the online questionnaires. Physical measures (anthropometrics, blood sample, DXA scan, functional fitness testing) will be completed. Those women in the wait-list control group will receive their introductory intervention session at this visit.

9 Study Analysis

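### Section 7.7.2 points data recovery for withdrawn women at pre-withdrawal data, so secondary measures taken only at baseline and week 10 become completers-only unless modelled, despite the stated intent to treat

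*Combined protocol and SAP*

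**What the plan says.** Section 7.7.2 describes what is sought from a woman who has withdrawn: "Data will be attempted to be gathered from participants who have withdrawn from the study to collect their data prior to their withdrawal". The next paragraph gives the analysis principle: "Withdrawn subjects will be analyzed using an intent to treat analysis, therefore maximizing the amount of data is paramount to success". A woman is lost to follow-up "if participants cannot be contacted after 3 attempts from the study team".

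Section 7.7.1 lists the reasons for withdrawal. They include "failure of subject to adhere to protocol requirements" alongside safety, loss to follow-up and withdrawal of consent. The only item that the protocol says should be sought after a woman leaves is in section 7.6.4, on revoked authorization: "attempts should be made to obtain permission to collect at least vital status".

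Section 8.1 gives the collection times for blood biomarkers, anthropometrics, DXA and functional fitness as "Baseline, final visit (~10 weeks"), and Table 3 agrees. Section 8.4.4 says "All participants will return for follow-up assessments at 10 weeks". Section 9.3.1 plans paired ANOVA and descriptive summaries for the functional and objective data. Section 10.2.1 leaves the handling of missing data to be chosen later, with sensitivity analyses or model-based methods as candidates.

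**The concern.** An intent-to-treat comparison needs an outcome for each randomised woman, or a stated method for those without one. For measures with a single follow-up time, data from before withdrawal cannot include that outcome.

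The plan also does not separate a woman who stops the exercises but would still come to a visit from one who withdraws permission to use or collect her data. Since non-adherence can count as withdrawal, a woman of the first kind can fall under the pre-withdrawal rule although her week-10 values were obtainable.

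At stake are the pre-post and between-group changes in the physical measures. If women who stop training benefit less than those who continue, completers give too favourable a picture of the exercise arm. Uneven loss is a risk that the protocol itself raises: section 14 names attrition in the treatment group as its second concern, while calling it less likely. A week-10 value that was never collected cannot be recovered later.

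**Working it through.** The plan has no figure of its own to reproduce: section 9.1 sets 40 women on feasibility grounds, without a power calculation.

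**Step 1. What pre-withdrawal recovery yields.** Take a woman who withdraws after the mid-point but before week 10.

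| Data | Times (sections 8.1 and 8.4) | Recoverable from before withdrawal |
|---|---|---|
| Exercise logs | Throughout | Yes, up to withdrawal |
| Questionnaires, accelerometer | Baseline, mid-point, week 10 | Baseline and mid-point |
| DXA, functional fitness, A1c/CRP, anthropometrics | Baseline, week 10 | Baseline only |

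In the last row she has no change score, and a paired analysis cannot use her.

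**Step 2. How many women.** Inputs: 40 women; about 5% loss expected (section 6.4.3); retention target above 90% (section 2.2); 1:1 allocation, so 20 per arm (section 8.4.1).

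- At 5% loss: 40 × 0.05 = 2 women.
- Most losses that meet the target: 3, since 37/40 = 92.5%. Four losses give 36/40 = 90.0%, which is not above 90%.
- Chance of at least one loss among 40 at a 5% rate: 1 − 0.95^40 = 0.87.

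**Step 3. Effect on the exercise arm's mean change.** Assume, since the documents give no figure, that withdrawn exercise women gain nothing and completers gain Δ on average. With a fraction d missing, the mean over all randomised women is (1 − d)Δ + d × 0 = (1 − d)Δ. Completers show Δ, so the ratio is 1/(1 − d).

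| Missing in exercise arm | d | 1/(1 − d) | Overstatement |
|---|---|---|---|
| 1 of 20 | 0.05 | 1.053 | about 5% |
| 2 of 20 | 0.10 | 1.111 | about 11% |
| 3 of 20 | 0.15 | 1.176 | about 18% |
| 4 of 20 | 0.20 | 1.250 | 25% |

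Two losses split evenly give the first row. Three losses all in the exercise arm give the third. The fourth row already misses the retention target.

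**Step 4. Check by simulation.** Baseline-adjusted comparison, 20 per arm, with assumed values not taken from the documents: true effect 0.5 SD, correlation 0.8 between baseline and week 10, no effect in withdrawn exercise women. With 1, 2 or 4 of 20 withdrawn, full follow-up gave 0.47, 0.45 and 0.40 SD; completers stayed near 0.50 SD. The ratios agree with step 3. The estimate's sampling standard deviation was about 0.19 to 0.20 SD, so the bias (0.03 to 0.10 SD) is smaller than the random error in a trial of this size.

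**The case against.** The strongest reply is that section 10.2.1 anticipates model-based handling and section 9.3 defines an all-randomised population. A likelihood or imputation analysis could keep women who have a baseline value only. A reader might infer from section 7.7.2 that intent to treat is impossible for these measures; the documents do not support that. What stands is that no method is fixed, that section 9.3.1 ties no analysis to the all-randomised set, and that any such method would rest on assumptions the data could not test.

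Second, the recovery rule suits the primary endpoint. Section 8.1 has the logs handed in at the final visit, so contacting a woman who left early to retrieve hers is sensible. Retention needs no measurement from her. This stands, and it confines the point to secondary data.

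Third, the sentence in section 7.7.2 is awkward, and the one after it stresses obtaining as much data as possible. It need not be a strict limit. A reader might also infer that sections 7.7.2 and 8.4.4 contradict each other. They do not: one covers withdrawn women and the other sets the visit schedule. Section 14 answers poor adherence with extra coaching, so stopping exercise is not automatically withdrawal. Yet no section says that a withdrawn woman is invited at week 10.

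Fourth, the consent form is a separate document (section 7.6.2) and may already draw the distinction. That cannot be checked here.

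**Conclusion.** The point holds for the measures taken only at baseline and about week 10. Followed as written, the plan leaves withdrawn women out of the planned paired analyses, and sections 7.7.1, 7.7.2 and 8.4.4 need to be reconciled. Questionnaires and accelerometry are less affected because they have a mid-point value. Adherence and retention are largely unaffected.

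The size is modest: about 2 of 40 women at the protocol's expected loss, with an overstatement of roughly 5% to 18% in the exercise arm's mean change for 1 to 3 women missing there, if withdrawn women gain nothing. A reader might take 25% as the likely bias. It needs four losses, all in the exercise arm, with no gain in any of them.

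A reader might also infer that these changes are meant to size the larger trial. Section 2.1 describes a field test of logistics and warns against relying on effects from small samples, and section 9.3.1 places the magnitude of expected changes among exploratory analyses. The estimates are therefore descriptive. The change is worth making because it is cheap and must precede the week-10 visits; it is not a threat to the trial's main aims.

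**What to change.** Amend section 7.7.2 to separate two groups: (a) women who stop the exercise programme, and (b) women who withdraw consent for data collection or cannot be reached.

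- Invite every woman in (a) to the already scheduled 10-week visit, with its $50 payment. If she declines the visit, ask for the online questionnaires and mailed accelerometer alone.
- Record the reason for any missing week-10 data.
- State in section 8.4.4 that its visit includes group (a), and in section 7.6.6 that the payment goes with attending the visit, since that section words the total in terms of completing the intervention.
- Align the consent form if it does not already say this.

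Nothing here alters the exercise prescription or any decision about when a woman should stop.

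The cost is amendment wording, possibly a consent sentence, and a few more coordinator contacts. Women who cannot be reached would still be missing, so the handling of their data under section 10.2.1 remains to be specified.

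A side benefit is that the exit interview takes place at the same visit, so women who stopped could be asked why.
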